6.2.8 Qualitative methods for mediation

Our Implementation Aim specifies: Specific Aim 3: Use mixed methods to explore implementation determinants and outcomes in the school intervention that promote effectiveness, fidelity and sustainability. We use the CFIR to guide our implementation determinants of interest which we are measuring both quantitatively and qualitatively. With regard to quantitative measurement, we are collecting school climate, leadership, and attitudes towards SBAT which are all determinants within the CFIR framework during implementation and sustainment. We also used the CFIR to inform our interview guides in querying around barriers and facilitators to implementation.

6.3 Statistical power for mediation analysis

The original study design included the following power calculations:

For this Aim, we rely on two programs contributed to the R statistical package. We again assumed 600 evaluable patients across 23 schools, and a design effect of about 2.5. In brief, David Kenny's program "PowMedR" (Kenny 2014) suggests that power is adequate to detect an effect size (in terms of standard deviations) of 0.25 sd for both the effect of the navigator intervention (A) on the mediator (M) and the effect of M given A on Y (conditional effect of M on outcome). Likewise, for the effects of school (S), with a design effect (variance inflation) of 2.5 (see estimate above based on ICC), power remains adequate for detecting an effect size of 0.5, which is the minimal important difference for asthma control For confirmation, the R package "medssp" (VIttinghoff 2015) suggests adequate power (greater than 0.8) to detect effect sizes of 0.25 jointly and separately for both the association of A (navigator) and M (effect of intervention M) and the effect of M on Y, and to detect effect sizes of 0.6 for the association of S (school based intervention) and M, the difference owing to the large design effect (variance inflation) arising from the clustered randomization of schools.

These calculations do not consider the impact of multiple comparisons and the change in the critical alpha level for these estimates. Power will quickly degrade with more than a few candidate mediators (updated 07/16/2019)

7. Analysis for implementation

See Penn IRB. (IRP PROTOCOL#: 830021. Adoption and Implementation of West Philadelphia Asthma Care Implementation Plan)

8. Power Calculations - revised 04/2019

Primary outcomes

Initial designs included formal statistical power calculations. Based on initial recruitment rates, the initial power calculation (for design and planning purposes) has been replaced by the following update (dtd 04/14/2019). Power calculations were done for planning purposes only, and they are here for historical record keeping purposes only. They are not appropriate once the study has been done. What happens if the number of children to be recruited falls below originally planned?

Factorial design		Child-level Intervention	
		A+	A-
School	S+	a	b
Level	S-	c	d
	none	e	f

The proposed design results in 6 groups of children. The cells a,b,c,d will permit comparison of any of the 3 combinations of school (S+) and child (A+) interventions (a,b,c) against the group that has neither(d). At the same time, it will permit marginal analysis of the effect of the school intervention (a+b vs c+d), and the marginal effect of the navigator intervention (a+c+e vs b+d+f).

For each of the cells of interest, we collect baseline data on children and then follow schools and children over time. This design avoids contamination and interference through cluster randomization, but benefits from added power of a longitudinal analysis. The factorial layout permits estimation (and testing) of interaction between the school and individual interventions. It also allows for use of data from children who are from nonparticipating schools.

This report focuses on the project power of a somewhat lower number of recruits in the 4 cells: a,b,c, and d, with a current projection of about 100 per cell (children) as contrasted with the prior expectations of 150 per cell. The design has also changed in that we now have more sites (expected 36 sites, with 18 in S+ and 18 in S-, the school-level intervention and controls.

As before, we could not rely on commercial power programs because of the complexity of the design – a convention randomization scheme crossed with a cluster randomized trial (school intervention). For that reason, we again report the results of simulation of the expected power given a stipulated "effect size" for the treatments (A+ and S+) at the child and school levels.

Another reason for the simulations is that we are interested in particular contrasts of interest in the effects of S+ and A+

Reviewing the prior assumptions from 2016 design.

Earlier power calcs were done by [name] by simulation, which posed a 2 by 2 factorial design with A=patient level and S=school level intervention. Estimates assumed a continuous outcome (such as asthma control) and improvement over time (to simplify the longitudinal data design).

We assumed factorial terms of A and S main effects and A*S interaction.

The main effects of A and S take into account that any interaction will affect the main effects. If the interaction is synergistic, then the "main effects" will be larger than just the A term or the S term alone. Main effects in this context are the marginal effects (of A and S), and these marginal effects are larger if there is a synergistic interaction (if the interaction is negative, then of course, the marginal effects are smaller).

We assume a design effect for the S+ S- effect (cluster randomized, and now 36 clusters (18+ 18)). If we assume effect size variation across sites (schools) of 0.0 to 0.5, then sd of random intercept is about 0.125. That would mean that if sigmasq= 1.0, then sigmasq(b) = 0.125*0.125. =0.016. If we assume that the variation in effect size is broader (0 to 1.0), then sd= 0.25 and sigmasq(b) = 0.25*0.25 = 0.0625. We used this broader assumption. Then ICC = 0.0625/(1.0625) = 0.06 and DEFF= 1+0.06*11 (assuming cluster size = 12) = 1+0.66= 1.66.

Plan is as follows.

Using program from Oct 2016, recreate power with 36 sites and 12 patients per site (n=432 overall). Results appear in the Table below.

Contrast	Contrast	Stipulated			Power	Power
	(Table cell)	Effect size(sd)			(n=600)	(n=432)
		А	S	A,S		
S+ v S-	a,b vs c,d	0.35	0.5	0.0	0.96	0.97
A+ v A-	a,c vs b,d	0.35	0.5	0.0	0.99	0.95
S+A+ v S-A+	a vs c	0.35	0.5	0.0	0.89	0.88
S+A+ v S+A-	a vs b	0.35	0.5	0.0	0.87	0.75
S- A+ v S-A-	c vs d	0.35	0.5	0.0	0.85	0.71
S+,A- v S-A-	b vs d	0.35	0.5	0.0	0.89	0.83
		А	S	A,S		
S+ v S-	a,b vs c,d	0.35	0.5	0.25	0.99	0.99
A+ v A-	a,c vs b,d	0.35	0.5	0.25	0.99	0.99
S+A+ v S-A+	a vs c	0.35	0.5	0.25	0.99	0.99
S+A+ v S+A-	a vs b	0.35	0.5	0.25	0.99	0.99
S- A+ v S-A-	c vs d	0.35	0.5	0.25	0.85	0.71
S+,A- v S-A-	b vs d	0.35	0.5	0.25	0.89	0.83

Power for contrasts of interest. Effect sizes are in terms of Cohen's d nomenclature and represents the fraction of standard deviations of change over time.

A=Navigator effect; S=School Effect; AS= interaction; "+" = , "-" = control

Cells e, f are not included in this table for simplicity and to be conservative.

Power to detect main effects

Power remains at acceptable levels for estimating the main effects and for some of the contrasts. Power is reduced, as one would expect, for contrasts that depend on the number of children enrolled. Power is not changed for the contrasts of the school effect, likely because of the increase in the number of schools enrolled and randomized. If there is an interaction (synergy) of School and Child interventions, power to show main effects (school or child interventions) will increase as will power in which the S+A+ cell is one of the contrasted cells.

Power to detect school*clinical synergy

Power is diminished and does not approach conventional levels to demonstrate an interaction (a formal statistical tests of synergy) of school and child interventions, unless the synergy is substantial (not show), but that contrast might not be of clinical interest.

Sparse data considerations.

In addition, power will be reduced if some schools enroll insufficient children to be able to make a contrast within school over time or across child treatment groups, or if a school enrolls no one.

9. Ancillary and unresolved issues

Our overall goal is estimation of the effects of the intervention, and the quantification of mediation, where applicable. To address conventional requests for tests of statistical significance, we will need to plan for statistical testing.

9.1 Multiple comparisons

Adjustments in critical levels for determining "statistical significance" when requested will follow these principles.

(a) If the contrast of interest is a primary or secondary outcome and pre-specified as such, we will make no adjustment

(b) All ad hoc, post SAP analyses and contrasts will be exploratory and hypothesis generating.

(c) All analyses for effect modification and mediation will consider the number of comparisons and make adjustments using simple Bonferroni correction for critical p-values.

9.2 Statistical power

It is very likely that all attempts to demonstrate heterogeneity of treatment effect and/or mediation will fail owing to inadequate numbers of patients spread over a large number of schools.

10. Update to Data Analysis Plan: Impact of Pandemic Restrictions. Presented to and approved by Data Safety Monitoring Board (DSMB) on 6/29/2021:

The original statistical analysis plan (SAP) includes the fitting of longitudinal models to evaluate the impact of study interventions on primary and secondary outcomes in models that model time as months from randomization, with splines (knots at 0, 3, 6, 9 and 12 months) and time by treatment interaction terms. Mixed-effects and population-averaged (GEE) models will be fitted.

The initial analyses will be conducted as planned. **Sensitivity analyses** will then be performed to evaluate the impact of pandemic restrictions (pre and post^{*}, where *Post = Time Period after March 14, 2020).

Longitudinal models for the main analyses will be modified to include an indicator variable for post COVID-19 phase* with time by post Covid-19 interaction and time by post COVID-19 by intervention interaction terms. In these models, post Covid-19 phase will be included as a time varying covariate within individuals.

Post pandemic restrictions by time by intervention interaction terms: If significant, the impact of an intervention at a particular time point (e.g., at 3 months post-randomization) depends on post pandemic status (relative to pre).

Post pandemic restrictions by time terms: If significant, the expected value of the outcome at a particular time point depends on post pandemic status (relative to pre).

Post pandemic restrictions indicator variable: If significant, the expected value of the outcome variables depends on post pandemic status (relative to pre).

References:

Berger VW. Pros and cons of permutation tests in clinical trials. Stat Med. 2000; 19(10):1319-28. [PMID: 10814980]

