### Secondary Outcomes:

- **Asthma Symptoms** will be measured using a 2 week recall diary at the baseline, 3 month, 6 month, 9 month and 12 month study visits.
- School Absences will be measured by school and parental report
- **ED visits and hospitalizations** for an asthma-related cause (ICD-9 493.XX) in the 12 months preceding the start of the study and the 12 months subsequent to study initiation, abstracted from the Epic medical record. We will assess for changes in ED and hospitalization usage following study enrollment.

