5.1.1 Outcomes

Outcome and their priority appear in Table 5.1.1

Table 5.1.1

Study Outcome-Listed	Measurement	3	6	9	12
in Order of Priority	times				
	(month) 0				
Asthma	Х	Х	Х	Х	Х
(Asthma control					
questionnaire)					
PRIMARY					
Asthma quality of life	Х				Х
Number of	Х				Х
hospitalizations					
Number of emergency	Х				Х
department visits					
On or off controller	Х				Х
medication					
Courses of oral steroids	Х				Х
Number of school	Х				Х
absences					
ICD-10 J45.XX	Х				Х
Diagnosis-based					
encounters- to define					
relevant office,					
hospitalization, ED					
visits					

School absences. Each child will have two semesters (one years) before and after the start of the intervention from which to calculate absences. Absenteeism data will ideally come from the

schools. If schools are unable to provide absenteeism data, self-reported data will be utilized. We propose to evaluate the reliability and completeness of school absences data before, and independently from, formal analysis of the association of this and other outcomes and treatment assignment.

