5.1.2 Measuring outcomes over time - irregular measurement times

Longitudinal model

Although the protocol calls for regular measurement times (Juniper's **Asthma Control Questionnaire** is a validated survey and will be administered by the CHW at baseline, 3 months, 6 months, 9 months and 12 months), in all likelihood these measurements will have the following characteristics. (1) They will not be administered at 3,6, 9 and 12 months. For some the schedule will lag. (2) Some children will miss one or more of these measurements.

Although some RCTs assume that measurements occur at the protocol-defined time, even when they do not, there is no reason for, and we shall deliberately avoid, that ad hoc practice.

We shall model the time of each measurement as the number of months (including factional amounts) from date of randomization. Time we shall model flexibly with splines. [Here we can use cubic splines as needed).

Choices for knots. We shall assume knots at time 3, 6 and 9 months, the intended dates of measurements.

With time measured flexibly, and with a statistical model that includes time by treatment (4 level) interactions, the spline model will allow for estimate of differences (or ratios) of outcomes at any point along the time (x) axis by treatment group.

Covariates -- selection and balancing

In theory randomization at the child level should balance on observed and unobserved factors. With children spread over 36 schools, and with chance differences across school, imbalances in child characteristics are possible at the school level but are not likely at the treatment assignment level (the four cells a, b, c and d). In addition, dropout can undermine the balance achieved in theory and in practice by randomization.

Key child-level covariates appear in Table 5.1.2.

Table 5.1.2 Covariates – baseline descriptions

Child level factors	Units of measurement or categories
AGE	Subgroups: 5-11; 12-13
GENDER	Male Female
Body mass index (weight in kg) (height in cm)	Collected and/or calculated by age-sex standardized percentile and/or z score. Both percentile and z will be used
HOUSEHOLD CHARACTERISTICS (descriptive only)	 (1) Single Parent/Caregiver vs Multiple Caregivers (2) Number of Adults in household (3) Number of Children in Household
Home environment	Number of bedrooms
Smoking	Smokers or none in home
Caregiver Education Highest level achieved by primary caregiver	Less than HS HS+ Graduate Level
Baseline Healthcare utilization	

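### SAP Section 10 has no rule for one-year counts that straddle 14 March 2020, and no single value of its 0/1 pandemic indicator is correct for them

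*SAP*

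**What the plan says.** SAP Section 10 concerns the longitudinal models that "evaluate the impact of study interventions on primary and secondary outcomes". It leaves the main analysis alone ("The initial analyses will be conducted as planned") and then adds a sensitivity analysis. A phase indicator is defined by "Post = Time Period after March 14, 2020", and the models are extended "with time by post Covid-19 interaction and time by post COVID-19 by intervention interaction terms". On coding, it says only that "post Covid-19 phase will be included as a time varying covariate within individuals".

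The time axis comes from SAP 5.1.2 (irregular measurement times): "We shall model the time of each measurement as the number of months (including factional amounts) from date of randomization".

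The outcomes differ in what a record covers:

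- **ACQ (primary):** SAP Table 5.1.1 marks it at months 0, 3, 6, 9 and 12.
- **Hospitalizations and ED visits:** Table 5.1.1 marks them at months 0 and 12 only. Protocol 5.4.1 counts them "in the 12 months preceding the start of the study and the 12 months subsequent to study initiation, abstracted from the Epic medical record".
- **School absences:** also months 0 and 12 only. SAP 5.1.1 says "Each child will have two semesters (one years) before and after the start of the intervention from which to calculate absences". If schools cannot supply the data, self-report is used, and Protocol 4.2.3 collects that as a two-week recall.
- **Oral steroid courses:** also months 0 and 12 only. SAP Table 5.1.2 gives a one-year look-back for the baseline value. No window is given for the month-12 value.

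**The concern.** A 0/1 indicator that changes with time suits a measure that describes the child at about the time of the visit. It does not suit a total built up over a year. When the year crosses 14 March 2020, part of the count arose before the restrictions and part after, and one binary value must mislabel one of the parts. Section 10 does not say how to treat such a record.

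This sensitivity model is the plan's only specified analysis of whether the restrictions changed the intervention effects, and Section 10 interprets each added term by its significance. A diluted interaction is harder to detect. SAP 9.2 already expects analyses of treatment-effect heterogeneity to fail for lack of numbers, so avoidable dilution matters. A distorted time-by-post term could also be taken for a real change in the course of utilization.

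**Working it through.** The plan gives no figure for this model, so there is nothing to reproduce. The check is calendar arithmetic.

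**Inputs from the documents.** Cut-off 14 March 2020 (SAP 10); counting windows of 12 months before and after (Protocol 5.4.1); records at months 0 and 12 (SAP Table 5.1.1). SAP 6.1.1 describes charter-school recruitment as substantial by December 2019, so children whose follow-up year crosses the cut-off exist. Their number is not stated.

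**Assumptions.** Windows run from each child's randomization. Enrolment is uniform, starting 18 to 24 months before the cut-off and ending E months after it (E = 0, 6, 12, 14). Event rates are constant within each phase. The indicator is set at the record's measurement time.

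**Step 1: one child.** For randomization m months before the cut-off (0 < m < 12), the pre-pandemic share of the follow-up count is m/12, and the record is coded post. By randomization date the share is 98% (20 March 2019), 75% (14 June 2019), 50% (14 September 2019), 25% (14 December 2019) and 8% (14 February 2020). About half of the straddling counts are therefore mostly pre-pandemic.

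**Step 2: month-12 records.** Those coded post come from 12 months of straddling enrolment (mean pre-pandemic share 0.5) and E months of later enrolment (share 0). Their mean share is p12 = (12 × 0.5)/(12 + E) = 6/(12 + E). Records coded pre are wholly pre-pandemic, so the post-minus-pre contrast keeps a fraction 1 − p12 of its true size. The intervention contrast keeps the same fraction on the additive scale, because the effect in a straddling count is share × pre-phase effect + (1 − share) × post-phase effect.

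**Step 3: baseline records.** These are coded post if the child was randomized after the cut-off. At e months after it, the look-back has pre-pandemic share 1 − e/12 (zero from 12 months on). The mean is p0 = 1 − E/24 for E up to 12, and 6/E beyond that.

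**Step 4: time-by-post.** Assume the restrictions halve the event rate equally at both times, so the true time-by-post ratio is 1. The apparent rate ratio in post-coded records is p + (1 − p) × 0.5.

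| E (months) | p12 | Month-12 contrast kept | p0 | Apparent ratio, baseline | Apparent ratio, month 12 | Month 12 / baseline (truth 1) |
|---|---|---|---|---|---|---|
| 0 | 0.50 | 50% | none coded post | – | 0.75 | – |
| 6 | 0.33 | 67% | 0.75 | 0.875 | 0.667 | 0.76 |
| 12 | 0.25 | 75% | 0.50 | 0.75 | 0.625 | 0.83 |
| 14 | 0.23 | 77% | 0.43 | 0.714 | 0.615 | 0.86 |

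The month-12 contrasts shrink, while the time-by-post ratio moves away from 1.

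**Step 5: coding by the start of the window.** Straddling follow-up counts would then be coded pre. With enrolment starting s months before the cut-off and continuing past it, pre-coded month-12 records have a mean post-pandemic share of 6/s, and the contrast keeps 1 − 6/s: 67% for s = 18 and 75% for s = 24. Choosing the other end of the window does not remove the problem.

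**The case against.** The best reply is that Section 10 never ties the indicator to a visit date. It defines post as a period of time, and its worked example (3 months after randomization) fits the ACQ schedule, not the counts. A reader might infer that the SAP prescribes visit-date coding; it does not. That reading is an inference from the time axis in SAP 5.1.2. This stands, and it means that what is documented is a missing rule. It does not dispose of the point, because Step 5 shows that a single 0/1 value is wrong for a straddling total whichever end of the window sets it.

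Four further limits stand:

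- **Which outcomes.** A reader might infer that all four count outcomes are affected. Only ED visits, hospitalizations and school-reported absences have documented one-year follow-up windows. The month-12 steroid window is undefined, and a 0/1 indicator is nearly exact for two-week-recall absences.
- **Mostly pre-pandemic.** A reader might infer that most straddling counts arose largely before the restrictions. Under uniform enrolment about half did.
- **Direction.** A reader might infer that every pandemic term shrinks toward zero. Step 4 shows otherwise for time-by-post.
- **Reach.** This is a sensitivity analysis. Section 10 says what a significant term means and claims no reassurance from a null one, so false reassurance would be a reader's inference, not the SAP's.

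**Conclusion.** The point holds as a gap in SAP Section 10 that should be closed. For ED visits, hospitalizations and school-reported absences, the 0/1 indicator cannot be correct for a total that straddles 14 March 2020, and no rule is given.

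If the indicator is set at measurement time, the month-12 pandemic and pandemic-by-intervention contrasts keep roughly 50% to 77% of their true size. The time-by-post ratio would appear as 0.76 to 0.86 when the truth is 1, for enrolment ending 6 to 14 months after the cut-off and an assumed halving of the event rate. Both ranges rest on uniform enrolment and constant rates within each phase. The documents give no enrolment calendar, so the direction of the month-12 dilution is firmer than its size.

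Nothing here supports a claim that the trial's main results are biased. The ACQ is not a one-year count, and the main analysis does not use the indicator.

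**What to change.** Add a coding rule to SAP Section 10 for interval counts, applied to both the baseline and the follow-up record:

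- **Dated events** (ED visits, hospitalizations, and school-reported absences where dated): either replace the 0/1 indicator with the proportion of the record's counting window that falls after 14 March 2020, or split both windows at that date and model the segment counts with log person-time as offset (enrolled school days for absences).
- **Undated events with a known window:** use the window proportion.
- **ACQ, other point-in-time measures and two-week recall:** keep the 0/1 indicator.
- **Steroid courses:** define the month-12 window first, then apply the matching rule.

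Under the assumptions above, splitting recovers the full contrast. The window proportion does so exactly on the additive scale and approximately under a log link: with half the window after the cut-off and a rate ratio of 0.5, the true mean ratio is 0.5 + 0.5 × 0.5 = 0.75, while the log-linear form gives √0.5 = 0.71. The proportion keeps two records per child. Splitting needs a stated rule for placing each segment on the months-from-randomization axis.

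The cost is SAP wording and some extra programming in a sensitivity analysis of secondary outcomes. ED visits and hospitalizations already come from the medical record, so no new data collection is needed for them.
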